- 1. The primary endpoint will be to prospectively investigate the efficacy of the nCAP Signal Relief Patch in reducing perioperative opioid requirement (up to 72 hours post-op) in opioid-naïve patients undergoing primary unilateral total hip or knee replacement surgery. Opioid requirement will be estimated following the placement of the patch.
- 2. The secondary endpoint will include the effects of nCAP Signal Relief Patch after the placement on postoperative pain, functional recovery, time to discharge from the hospital, and opioid related complications, such as, PONV, itching, sleep disorders, respiratory depression, and urinary retention.

Study Design

The proposed pilot study will be conducted as a single-center prospective, randomized, open label trial at the University of Pittsburgh Medical Center (UPMC) Shadyside Hospital.

Institutional review board approval will be obtained before eligible patients are recruited and consented. The trial will be registered at www.clinicaltrial.gov before beginning recruitment.

The efficacy of this device will be established by comparing postoperative opioid requirement to maintain pain scores \leq 4 using a Numerical Rating Scale (NRS). Accordingly, pain will be treated according to the following protocol: pain scores \leq 4, non-opioid analysics, pain scores between 4 and 6 oxycodone 5 mg q 4 hrs and \geq 7, oxycodone 10 mg, Hydromorphone IV 0.2-0.5 mg q 3 hr. Data collected following the placement in the treatment group (Standard of Care ERAS protocol + nCAP Signal Relief Patch) will be compared to the data obtained in the control group (Standard of Care ERAS protocol).

Recruitment

Potential subjects may be given a recruitment flyer (attached) in the office of surgeons Drs.

[name], [name], or [name]. The potential subjects who receive a flyer will then have the option of contacting the study team to discuss the study further, or, if they express interest in participating in the surgeon's office, their name will be given to the study team from the surgeon's office staff.

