Potential subjects may also be identified by the study team who has normal access to the Operating Room Schedule and electronic medical records. If a subject is deemed eligible via inclusion/exclusion criteria, a study team member will approach them the morning of their scheduled surgery and discuss the study with them at length and answer any questions they may have. If a potential subject is willing to sign consent, then a physician investigator will be available to review the consent, risks and benefits of participation, and obtain informed consent.

If our research team is contacted prior to the day of surgery, or if we reach out based upon the list of interested potential subjects, study team will discuss the study at length over the phone and answer any questions the potential subjects may have. Subjects interested in participating will be emailed the currently approved informed consent form to review. They will be given the option to sign consent electronically for convenience via REDCap or they can sign consent form on the day of surgery in the pre-operative holding area.

The subject will be approached as soon as they arrive to the hospital (at least 2-3 hours before their surgery) and will be given adequate time to consider the consent and ask questions. The patient will be urged to take as long as necessary to decide whether or not to participate. If the

subject feels they do not have enough time to make a decision, they will not be enrolled in the trial.

All questions will be addressed and it will be made clear that the patient may withdraw from the study at any time. Investigator physician will sign the informed consent with the patient prior to beginning of any study procedures.

Randomization Process

Participating patients will be randomized by computer-generated random numbers to either the control group (standard of care ERAS protocol) or intervention group (nCAP Signal Relief Patch group+ ERAS protocol).

Inclusion Criteria:

- Over 18 years of age
- Scheduled for elective primary unilateral hip or knee replacement surgery

Exclusion Criteria:

- Active clinical depression, anxiety, or catastrophizing
- Raw score equal to or greater than 19 on the PROMIS Anxiety 8a Adult v1.0
- Active alcoholism or drug abuse
- Severe chronic pain condition that requires daily preoperative opioid dependence
- Total surgery revision, bilateral hip replacement, multiple surgeries

Treatment Groups

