Each subject will undergo surgery and anesthesia using the approved ERAS protocol.

Control Arm (n=30): Control group will receive approved ERAS multimodal anesthesia protocol (standard of care).

Interventional Arm (n=30): Intervention group will receive approved ERAS multimodal anesthesia protocol plus an nCAP Signal Relief Patch.

Data Collection and Outcome Measures

After signing an informed consent, subjects will complete the PROMIS Emotional Distress – Anxiety – Short Form 8a before completing any other questionnaires. Subjects who have a raw score <19 will be enrolled in the study. Any subject who scores \ge 19 will be considered a screen failure and excluded from the study.

Once the subject is enrolled, they will be asked to complete the Pain Catastrophizing Scale (PCS), the PROMIS® Emotional Distress-Depression - Short Form 8a, and the PROMIS® Item Bank v1.0 – Sleep- Disturbance – Short Form 8a prior to surgery. The subject will also conduct a baseline functionality test to assess mobility and strength in their leg. The functional recovery will be assessed by determining the patient ability to walk 100 feet, go up 5 steps and raise their leg on the day of surgery. Scores can be 0 (no ability to raise the leg), 1 (some ability to raise the leg), and 2 (complete ability to raise the leg).

Once these assessments are completed, subjects will be equally randomized to the intervention group (nCAP signal relief Patch + standard of care) or control group (standard of care). Both the control group and intervention group will receive approved ERAS multimodal standard of care. Only the interventional group will receive an nCAP Signal Relief Patch.

Randomization will occur by assigning the participant a subject ID number, and this ID number will correspond to a treatment allocation based on a pre-designed randomization schema.

Subjects will undergo surgery using the approved ERAS anesthetic and post-operative pain management protocols.

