After surgery, the subjects randomized to the intervention group will have the nCAP Signal Relief patch applied to their surgical dressing by a trained researcher in the immediate Post Anesthesia Care Unit (PACU). Subjects will be made aware at the time of consent and throughout the trial that they can drop out of the study at any time if they do not like wearing the nCAP Signal Relief Patch. The control group will not receive a patch but will receive the standard of care ERAS protocol. Subjects in the intervention group will be instructed to keep the nCAP Signal Relief Patch on their surgical dressing to avoid the risk for skin irritation.

Pain using a Numerical Rating Scale (NRS) at rest and with movement as well as opioid requirement will be assessed in the PACU and daily until discharge.

Subjects assigned to the intervention group should keep the nCAP Signal Relief Patch in place for 72 hours on their surgical dressing and they will be instructed to remove it at home.

Once the subject is discharged, they will be asked to complete a pain and opioid diary to record pain-related outcomes. They will be contacted via email (REDCAP survey) on post-operative day 1,2,3, 7, 14, and 30 to record postoperative opioid consumption, non-opioid consumption, NRS pain at rest and with movement, pain catastrophizing (via Pain Catastrophizing Scale) sleep quality (via PROMIS Sleep Disturbance Short Form 8a) and to assess functional recovery. Functional recovery will be assessed by determining the patient ability to walk 100 feet, go up 5 steps and raise their leg on postoperative days 1, 2, 3, 7, 14, and 30 as well as the pain associated with it. Patient satisfaction with pain management after surgery will be assessed at the 30 day follow up (0- least satisfied to 10-most satisfied). Subjects who are contacted via REDCap to complete follow-up questionnaires and do not complete them on the day they are assigned will be contacted via telephone for a reminder. They will be considered lost to follow up after 3 phone attempts.

Information will be collected from the medical record, including: patient demographics, medical history, medication summary while in the hospital, as well as progress notes from the entire encounter to determine the existence of adverse events.

Pre-and-Post Metric Evaluation

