Study Title: A Pilot Study Investigating the nCAP Signal Relief Patch in Subjects Undergoing Primary Hip or Knee Replacement Surgery – A Pilot Trial

Principal Investigator: [name], PhD, MBA

IRB: STUDY22010018 NCT: 05252858

Statistical Analysis Plan Approval Date: 02/01/2022

Power calculation is for an anticipated 60 subjects who underwent TKA. Data is to be analyzed using intend-to-treat analysis plan. Data collection in this study includes the following measurements:

- Total opioid consumption (OME mg),
- Pain at rest and during movement rated on a standard Numerical Rating Scale (NRS, 0 = no pain and 10 = the worst pain imaginable),
- Area under the curve (AUC) for pain scores collected on POD 1, 2, 3, 7, 14, and 30,
- Time to discharge from the recovery room,
- Time to discharge from the hospital, and
- Overall subject satisfaction at the time of hospital discharge

The number of subjects requesting a prescription refill during the first 30-days post-operative will be calculated using the Pennsylvania Data Management Program.

Student's t-test, non-parametric Kruskal-Wallis test, or Pearson's chi-square test were used to determine differences in the distribution of continuous outcomes, and the chi-square test or exact test was used for differences in proportions for categorical outcomes between the treatment and placebo arms. Data will be presented as mean \pm standard deviation (SD) with a standard alpha set at 0.05.

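### Dislike of the patch is offered as a reason to leave the study, a reason only the patch arm can have, with no provision for follow-up after early removal under the stated intention-to-treat analysis

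*Protocol*

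**What the plan says.** In Data Collection and Outcome Measures the protocol has subjects informed, both when they consent and repeatedly afterwards, of this option: "they can drop out of the study at any time if they do not like wearing the nCAP Signal Relief Patch". No arm is named. The same section places randomization after consent and baseline testing: "Once these assessments are completed, subjects will be equally randomized to the intervention group". It adds: "Only the interventional group will receive an nCAP Signal Relief Patch", and of the other arm: "The control group will not receive a patch but will receive the standard of care ERAS protocol".

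Separately, Recruitment gives every patient a general right: "it will be made clear that the patient may withdraw from the study at any time".

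The primary endpoint (Specific Aims) is opioid requirement up to 72 hours after surgery. The patch is meant to stay on for the same 72 hours and then be removed at home. In-hospital medication comes from the medical record. After discharge, opioid use, pain, function and sleep come from a diary and from surveys on days 1, 2, 3, 7, 14 and 30.

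On analysis principle the SAP has one sentence: "Data is to be analyzed using intend-to-treat analysis plan". It does not define the analysis set and has no rule for withdrawals or missing outcomes.

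**The concern.** The only response to disliking the device that the protocol names is leaving the study. Taking the patch off and continuing with assessments is not described anywhere. Because the trial is open label and one arm has no device, this prompt has practical meaning in one arm only, and it is repeated after allocation.

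Intention-to-treat needs outcomes from everyone randomized, including those who stop the device. If leavers supply no further data, the analysis becomes a comparison of those who stayed. If subjects who get poor relief are the ones who tire of the patch, those remaining in the patch arm would show lower opioid use even if the patch did nothing. The protocol says these pilot data will support a proposal for a full-scale trial, so a spurious reduction would carry forward.

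**Working it through.** **Which outcomes are exposed**

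1. Opioid use up to discharge is assessed in hospital and held in the medical record for both arms, so it is largely protected.
2. Opioid use from discharge to 72 hours is exposed. Removal at home at 72 hours, a post-discharge opioid diary and surveys on days 1 to 3 show that the protocol expects discharge before the window closes. The share of the 72-hour total that falls after discharge cannot be computed, because no length of stay is given.
3. Pain AUC to day 30, function, sleep and day-30 satisfaction are exposed, since they depend mainly on follow-up contacts that a leaver would not complete.
4. Prescription refills come from a state data program and may survive withdrawal.

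**Figures in the plan.** There are 30 per arm (Treatment Groups), 60 in the SAP power statement, and alpha 0.05. The 60 cannot be reproduced, because no effect size, SD, power or dropout rate is stated. For scale, 30 per arm at two-sided 0.05 gives 80% power for (1.960 + 0.842) × √(2/30) = 0.72 SD.

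**Illustration A: mean shift.** Assume a share d of the patch arm leaves, and that leavers' unseen outcomes are g SD higher than those of stayers.

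- Bias = d × g (in SD).
- SE = √(1/30 + 1/[30(1 − d)]).
- Two-sided type I error = 1 − Φ(1.96 − bias/SE) + Φ(−1.96 − bias/SE).

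| d | SE | g | Bias (SD) | Type I error |
|---|---|---|---|---|
| 10% | 0.265 | 0.5 | 0.05 | 5.4% |
| 10% | 0.265 | 1.0 | 0.10 | 6.6% |
| 20% | 0.274 | 0.5 | 0.10 | 6.5% |
| 20% | 0.274 | 1.0 | 0.20 | 11.3% |

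**Illustration B: skewed opioid totals.** Assume no true effect, lognormal 72-hour totals with CV 0.8, 30 per arm, leavers in the patch arm only, each leaver's whole total deleted, and a rank-sum test (the two-group form of the SAP's Kruskal-Wallis option).

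Hand check of the false reduction:

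- σ = √ln(1 + 0.8²) = 0.703.
- The upper half of this distribution averages 2Φ(0.703) = 1.518 times the overall mean.
- Three upper-half leavers: (30 − 3 × 1.518)/27 = 0.942, a false reduction of about 6%.
- Six upper-half leavers: (30 − 6 × 1.518)/24 = 0.870, about 13%.

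Simulation (40,000 trials) agrees and adds the type I error:

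| Leavers | Who leaves | False reduction | Type I error |
|---|---|---|---|
| 3 of 30 | random, upper half | 6% | about 6% |
| 6 of 30 | random, upper half | 13% | about 10% |
| 3 of 30 | the highest users | 19% | about 10% |
| 6 of 30 | the highest users | 30% | about 24% |
| 3 or 6 | random, whole arm | none | not raised |

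Deleting the whole total ignores the in-hospital opioid data that the record would still hold, so these figures are an upper bound for the leavers assumed.

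**The case against.** The strongest reply is that the sentence is an ordinary statement of voluntary participation. It is addressed to subjects in general, first at consent and so before allocation, and Recruitment gives everyone the right to withdraw. A reader might infer that only patch-arm subjects are told they may leave. The documents do not support that: the offer is common to both arms, and only the patch-specific motive is one-sided. Nor is a right to withdraw a flaw.

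A reader might also infer that taking the patch off ends data collection. No text says so. The documents are silent on it, and a stated intention-to-treat principle would ordinarily keep such a subject in the assigned arm. This objection stands against the stronger claim. It does not remove the gap, because leaving the study is the only course named and nothing tells staff to continue follow-up.

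Third, chart data cover the hospital stay, so at most the post-discharge part of the primary outcome is exposed. That is right, and it limits the loss.

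Fourth, the direction is not documented. Dislike of wearing the patch may be plain discomfort unrelated to opioid use, and controls in an open-label trial may also leave on learning that they get no patch. Both points are fair. The calculations show what could happen under stated assumptions; they do not predict the result.

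**Conclusion.** The point holds in a limited form. The protocol ties dislike of the patch to leaving the study, the reason can apply in one arm only, and neither document provides for follow-up after early removal. One-sided, outcome-related missing data are therefore possible for the post-discharge part of the primary outcome and for the later survey outcomes, and the SAP's intention-to-treat sentence does not deal with them.

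The size is unknown. With few leavers, or leaving unrelated to outcome, the effect is small or absent: 3 upper-half leavers move type I error from 5% to about 6%. It becomes material at about 20% one-arm loss related to opioid use, with a false reduction of 13% and type I error of about 10%. The figures of 30% and 24% require exactly the six highest users to leave, all from the patch arm, with their chart data discarded. A reader should not take those as expected values. Leaver numbers, CV, distribution and selection are all assumptions.

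The change is worth making because it is cheap and removes an avoidable source of bias. Confidence is moderate.

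**What to change.** **Protocol, Data Collection and Outcome Measures (and matching consent text).** Replace the drop-out sentence with wording to this effect:

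> A subject who stops wearing the patch is not thereby withdrawn from the study. Scheduled opioid, pain and function assessments continue with the subject's agreement. The time of and reason for removal are recorded. Withdrawal from data collection is a separate decision, under the general right described in Recruitment.

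This sets no rule on when the patch may be removed and leaves the right to withdraw unchanged.

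**SAP.** State that all randomized subjects are analysed in their assigned arm and that data collected after patch removal are included. Say also how a 72-hour total is handled when only its in-hospital part is known.

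**Cost.** Wording changes, one data field for removal time and reason, and a few subjects still receiving surveys after taking the patch off. Sample size and schedule do not change.

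### Skin reactions to the patch are looked for only in hospital progress notes, although the patch comes off at home; no survey item or SAP outcome covers them, and itching has no attribution rule

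*Protocol*

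**What the plan says.** **The risk and its mitigation.** In the protocol, Data Collection and Outcome Measures, a trained researcher places the patch on the surgical dressing in the recovery unit, and subjects are told to "keep the nCAP Signal Relief Patch on their surgical dressing to avoid the risk for skin irritation".

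**Exposure.** The intended wear is 72 hours. Removal is left to the subject after discharge: "they will be instructed to remove it at home".

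**Adverse events.** The same section draws on the medical record, including "progress notes from the entire encounter to determine the existence of adverse events". No other source of adverse events is described.

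**Scheduled checks.** In hospital, pain and opioid requirement are assessed in the recovery unit and then daily. After discharge, the surveys on days 1, 2, 3, 7, 14 and 30 are "to record postoperative opioid consumption, non-opioid consumption, NRS pain at rest and with movement, pain catastrophizing", plus sleep and function, with satisfaction added on day 30. Neither list contains a skin, wound, itching or general adverse-event item.

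**Itching.** Specific Aims, item 2, places it among "opioid related complications, such as, PONV, itching, sleep disorders, respiratory depression, and urinary retention". No source, timing, body site or attribution rule is given.

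**Analysis.** The SAP list that opens "Data collection in this study includes the following measurements" has opioid consumption, pain, pain AUC, two discharge times and satisfaction. It also counts prescription refills. For categorical data it says only that "the chi-square test or exact test was used for differences in proportions for categorical outcomes"; no safety outcome is named.

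**The concern.** The protocol names one local harm of the device, yet the observation of that harm can end before the exposure does. Discharge closes the hospital notes, while the patch may stay on until hour 72 and is removed without a staff check. The surveys do reach the subject in this window, but as listed they do not ask about it.

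Two conclusions are at stake. The first is local tolerability. The protocol (Pre-and-Post Metric Evaluation) says the pilot data will support a proposal for a full-scale placebo-controlled trial, and silence from unsolicited reporting could be read there as evidence of safety. The second is the itching part of the secondary endpoint. If the patch spares opioids, generalised itch should fall; if it irritates the skin, local itch should rise. Only the patch arm can have patch-site itch, so an undifferentiated itching count could combine two effects with opposite signs.

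**Working it through.** The plan states no figure on this point, so there is none to reproduce. The check sets observation against exposure and then asks what 30 patch subjects could show.

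**1. Observation against exposure**

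| Period | Patch on? | Stated way to detect a skin reaction |
|---|---|---|
| Recovery unit to discharge | Yes | Progress-note review, if staff chart it |
| Discharge to hour 72 | Yes | None listed |
| Removal at home | Comes off | None listed |
| After removal, to day 30 | No | None listed |

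This reads the encounter as the hospital stay. The surveys on days 1, 2, 3 and 7 span wear and removal, so the contact points exist and only the question is missing.

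**2. What zero events would mean**

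Input: n = 30 in the patch arm (protocol, Treatment Groups). With 0 events in n subjects, the exact two-sided 95% upper limit solves (1 − p)^n = 0.025:

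p = 1 − 0.025^(1/30) = 1 − 0.8843 = 11.6%.

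The one-sided 95% limit is 1 − 0.05^(1/30) = 9.5%. Both require that every subject was assessed. If only a fraction c of reactions is captured, the limit applies to c × p. With c = 0.5 (assumed), 0 of 30 is compatible with a true rate up to 11.6% / 0.5, or about 23%.

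**3. Chance of seeing at least one reaction**

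Formula: 1 − (1 − c × p)^30. The true rates p and capture fractions c are assumed; the documents give neither.

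| True rate p | All captured (c = 1) | Half captured (c = 0.5) | Quarter captured (c = 0.25) |
|---|---|---|---|
| 1% | 26% | 14% | 7% |
| 2% | 45% | 26% | 14% |
| 5% | 79% | 53% | 31% |
| 10% | 96% | 79% | 53% |

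A pilot of this size would probably reveal a reaction rate of 5% to 10% if it asks everyone, and is much less sure to do so if it does not.

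**4. Between-arm testing**

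By Fisher's exact test against 0/30 in controls, 5/30 gives p = 0.052 and 6/30 gives p = 0.024. A test would need six reactions (20%) to reach 0.05, so description with intervals is the sensible analysis.

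**5. Itching: illustration only**

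Assume 20% itch in controls, 10% opioid itch in the patch arm, and patch-site itch at rate s, independent of opioid itch. The patch-arm total is 1 − (1 − 0.10)(1 − s).

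| s | Patch-arm total | Patch minus control |
|---|---|---|
| 0% | 10.0% | −10.0 points |
| 5% | 14.5% | −5.5 points |
| 10% | 19.0% | −1.0 point |
| 15% | 23.5% | +3.5 points |

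Pooling could shrink or reverse a true reduction. Every rate here is assumed, and the calculation supposes that local itch is recorded and not separated.

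**The case against.** The strongest objection is that adverse events are in fact collected. A reader might infer that skin harm goes entirely unrecorded. The documents do not support that: the progress-note review covers any reaction that staff chart before discharge. This objection stands and limits the point to capture that is passive, not specific to skin, and confined to the encounter.

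Second, the patch goes on the dressing and not on the skin, expressly to prevent irritation, so the rate may be very low. This also stands as a reason to expect few events. It does not show that the mitigation works, since it relies in part on subjects following an instruction and nothing listed measures the result.

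Third, a reader might infer that local itch would be scored as an opioid complication and would cancel a real benefit. The documents do not go that far. They give no source or scoring rule for itching, notes may record site and cause, and the SAP does not name itching, so no specified comparison is corrupted. If itching is never solicited, little local itch may enter the count at all. That itch can be a sign of irritation is a reasonable inference, but the documents do not say so. Nor could this pilot establish a 10-point itching difference even with perfect attribution: for an assumed 20% against 10% with 30 per arm, power is about 10% by Fisher's test and 19% by the uncorrected chi-square test. What remains is an ambiguity in the endpoint definition.

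Fourth, the 11.6% limit reflects sample size, and better data capture will not lower it. True; but the limit can be quoted only if all subjects were asked.

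**Conclusion.** The concern holds in a limited form. For a risk the protocol itself names, detection depends on hospital notes, nothing is solicited after discharge although removal is planned at home, and the SAP has no safety outcome. Reactions at home or at removal can be missed, and zero recorded events could not be presented as tolerability. With full ascertainment, zero in 30 would still leave a rate of up to 11.6% possible; with incomplete ascertainment the bound is higher by an unknown amount.

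The itching issue is secondary: a possible mixing of two causes, of unknown size, arising from the protocol's endpoint wording and not from any named SAP test. The primary opioid endpoint is unaffected.

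This rests on the survey and measurement lists being complete as written, and on the encounter meaning the hospital stay.

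**What to change.** - **Data collection.** In both arms, add one yes/no item to the existing in-hospital daily check and to the day 1, 2, 3 and 7 surveys: any redness, blister, itch or wound problem at the dressing site. Asking controls as well supplies the background rate from the dressing and wound.
- **Itching.** Wherever itching is recorded, note whether it is at the dressing or elsewhere, so that the opioid-related endpoint can be reported without dressing-site itch.
- **SAP.** Add a descriptive table of local skin and wound events by arm, giving the number of subjects asked, the number with an event and the exact 95% interval. No hypothesis test is needed.

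The cost is slightly longer surveys, one extra field and one more table. The sample size, contact schedule and treatment are unchanged.

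### No pre-operative pain score is scheduled, and the post-placement rule is not turned into a timed PACU score with a matching time zero for controls

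*Protocol*

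**What the plan says.** **Before surgery** (Protocol, Data Collection and Outcome Measures). After the PROMIS anxiety screen, enrolled subjects fill in further questionnaires: "they will be asked to complete the Pain Catastrophizing Scale (PCS), the PROMIS® Emotional Distress-Depression - Short Form 8a", and the PROMIS sleep form. A function test follows: "The subject will also conduct a baseline functionality test to assess mobility and strength in their leg". No NRS is listed here, and pain linked to function is recorded only on the postoperative days. Randomization comes after these assessments and before surgery.

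**In the PACU** (same section). A trained member of the study team puts the patch on the dressing. The pain schedule reads: "Pain using a Numerical Rating Scale (NRS) at rest and with movement as well as opioid requirement will be assessed in the PACU", and then daily until discharge. No arrival score, interval or clock time is given.

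**Which data count** (Protocol, Study Design and Specific Aims). Study Design compares "Data collected following the placement in the treatment group" with the data from controls. The second aim concerns "the effects of nCAP Signal Relief Patch after the placement on postoperative pain".

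**Analysis** (SAP). The SAP lists NRS at rest and during movement, and a pain AUC over postoperative days 1, 2, 3, 7, 14 and 30. The between-arm tests are unadjusted. There is no covariate and no change-from-baseline analysis.

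**The concern.** Catastrophizing, sleep and function each have a pre-operative value and are followed up after surgery. Pain, the symptom that the patch targets, is followed on the same days without one. Three things are at stake.

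- **Precision.** In a trial with 30 per arm, a correlated baseline covariate is one of the few cheap ways to sharpen the pain comparison. This plan has none to use.
- **Visibility of imbalance.** Hips and knees are enrolled together, and the protocol states no stratification. If the arms start with different pain, nobody will be able to see it or adjust for it.
- **The PACU time point.** Pain changes as anaesthesia wears off. A PACU score means the same thing in both arms only if it is taken at a comparable moment, and the plan fixes no such moment.

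The protocol (Pre-and-Post Metric Evaluation) also says that the pilot will support a proposal for a full-scale trial. Without a pre-operative NRS, the pilot cannot estimate the correlation between baseline and outcome pain, which would help to size that trial.

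**Working it through.** **1. The schedule, side by side** (Protocol, Data Collection and Outcome Measures)

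| Measure | Before surgery | After surgery |
|---|---|---|
| Catastrophizing (PCS) | yes | days 1, 2, 3, 7, 14, 30 |
| Sleep (PROMIS 8a) | yes | same days |
| Function | yes | same days, with associated pain |
| NRS at rest and with movement | **no** | PACU, daily until discharge, same days |

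**2. The plan's own figure.** The SAP ties 60 subjects to a power calculation but gives no effect size, SD or power, so the figure cannot be reproduced. Working backwards with 30 per arm and alpha 0.05 (taken as two-sided, which the SAP does not state), by normal approximation:

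- 80% power: (1.960 + 0.842) × sqrt(2/30) = 2.802 × 0.258 = 0.72 SD
- 90% power: 0.84 SD

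**3. Unseen imbalance in starting pain.** The SE of a baseline difference is sqrt(2/30) = 0.258 SD, with a 95% range of ±1.96 × 0.258 = ±0.51 SD. With an assumed NRS SD of 2.5, the SE is 2.5 × 0.258 = 0.645 points. The probability of a chance difference of at least 1 point is 2 × (1 − Φ(1/0.645)) = 2 × (1 − Φ(1.55)), or about 12%.

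**4. Precision given up.** With a pre-operative NRS as covariate, the residual SD is multiplied by sqrt(1 − r²), where r is the correlation with later NRS. The documents give no r, so a range is shown.

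| r (assumed) | Variance removed, r² | SE factor | Detectable at 80% power | Power at 0.72 SD |
|---|---|---|---|---|
| 0 | 0% | 1.00 | 0.72 SD | 80% |
| 0.2 | 4% | 0.98 | 0.71 SD | 82% |
| 0.3 | 9% | 0.954 | 0.69 SD | 84% |
| 0.5 | 25% | 0.87 | 0.63 SD | 90% |
| 0.6 | 36% | 0.80 | 0.58 SD | 94% |

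For r from 0.3 to 0.6, the SE falls by about 5 to 20%.

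**5. The PACU score.** Study Design starts the patch arm's data at placement. Data Collection and Outcome Measures puts placement and the first NRS in the same unit without an interval between them. Controls have no placement, and no substitute event or time is named for them. The post-placement rule therefore cannot be applied alike in both arms as written.

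To show what firm timing protects, suppose that the rule slipped and a share f of patch-arm PACU scores was taken before application. The effect at that time point would shrink to (1 − f) × 0.72 SD:

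| f (assumed) | Effect seen | Power |
|---|---|---|
| 0 | 0.72 SD | 80% |
| 10% | 0.65 SD | 71% |
| 25% | 0.54 SD | 56% |
| 50% | 0.36 SD | 29% |

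Nothing in the documents says that f exceeds zero. The SAP's pain AUC begins on postoperative day 1 and is untouched by this.

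**The case against.** A reader might infer that the first pain comparison is not a post-treatment comparison, or that it is biased. The documents do not support this. Study Design limits the patch arm to data obtained after placement, and the second aim is worded the same way. A score taken before the patch is thus outside the planned comparison. The protocol also describes application before it describes the PACU assessment. What is missing is an operational time, not a definition.

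A reader might also infer that controls are scored at a different stage of recovery because no researcher comes to apply a patch. That is not in the documents either. The PACU score is scheduled without distinguishing the arms, and the protocol does not say who records it in either arm.

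On the baseline, the fair reply is that randomization protects the comparison without one. Chance imbalance is already reflected in the standard error and in alpha, and the 12% figure would apply to any unmeasured covariate with that SD. The SAP claims no change-from-baseline analysis. At r = 0.3 the gain in SE is only 5%.

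All of this stands, and it confines the point to precision, description and one time point. It does not supply a time zero for controls. Nor does it explain why pain alone lacks the pre-operative value that the other followed-up scales have.

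**Conclusion.** The point holds in a limited form. The absence of a pre-operative NRS and of a timed PACU score with a matching time zero for controls is plain from the text. It does not bias the randomized comparison of pain on postoperative days 1 to 30. Its reach is as follows:

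- an SE that could be about 5 to 20% smaller, if r lies between 0.3 and 0.6;
- starting pain that cannot be compared between arms of 30, where chance alone would give a difference of 1 point or more in about 12% of trials, if the SD is 2.5;
- a PACU time point, within a secondary endpoint, that is hard to interpret.

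The values of r, SD and f are assumptions. The change is worth making because it is cheap and because a pre-operative rating cannot be recovered once a subject has had surgery. It is not a validity error.

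**What to change.** 1. **Protocol, pre-operative assessments.** Add NRS at rest and with movement to the existing questionnaires, before randomization.
2. **SAP.** Name this score as the prespecified covariate in the NRS and pain AUC comparisons, and in a supportive comparison of opioid consumption (OME).
3. **Protocol, PACU assessment.** Take the PACU outcome NRS at one fixed interval after PACU arrival in both arms, after the patch has been applied in the intervention arm. Arrival is an event that both arms share; placement is not.
4. **Any score at PACU arrival** should be descriptive only. It may look like the natural baseline, but it follows randomization in an open-label trial, so a difference between arms could reflect knowledge of allocation. It should not be a covariate.

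**Cost.** One extra short rating occasion before surgery, when subjects are already completing questionnaires; a minor protocol amendment; and a short addition to the SAP. If the correlation turns out low, little precision is gained: at r = 0.2 the detectable difference moves only from 0.72 to 0.71 SD.
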